9.2 SETTING

A log of all patients included into the study (i.e. having given informed consent) will be maintained in the ISF at the investigational site.

Boehringer Ingelheim reserves the right to discontinue the study overall or at a particular study site at any time for the following reasons:

1. Failure to meet expected enrolment goals overall or at a particular study site
2. Any administrative reasons that could significantly affect continuation of the study according to signed site contract
3. Violation of GCP, the CTP, or the contract by a study site or investigator, disturbing the appropriate conduction of the study

The investigator / the study site will be reimbursed for reasonable expenses incurred in case of study termination (except in case of the third reason).

All patients, both female and male gender, referring to pulmonary centers will be consecutively enrolled according to the following criteria:

Inclusion Criteria

7. Patients aged ≥ 40 years
8. Patients must have a documented diagnosis of chronic obstructive pulmonary disease (COPD)
9. Patients with no exacerbations in the last 3 months
10. Patients requiring regular treatment according to GOLD guidelines, i.e.: undergoing stable pharmacological treatment for COPD since at least 3 months
11. Written informed consent to both participation in the study and privacy form
12. Patients capable of discernment and able to read or write in Italian language.

Exclusion Criteria

4. Patients who are currently participating in a clinical trial on experimental drugs.
5. Patients naïve to pharmacological treatment for COPD
6. Diagnosis of Asthma COPD Overlap Syndrome (ACOS)

Study Exit criteria

An individual patient may be withdrawn from the non-interventional study prior to completion if any of the following criteria apply:

4. The patient withdraws consent, without the need to justify the decision.
5. The patient is no longer able to participate (according to clinical judgment)
6. Administrative reasons (inclusion in another clinical trial)

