2.4 Safety set

All enrolled patients meeting the inclusion criteria #4 and #5 and not meeting the exclusion criteria #7, #8 and #9 (i.e. all enrolled subjects who provided informed consent to both participation in the study and privacy form, requiring regular treatment according to GOLD guidelines) will be included in the safety analysis.

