- Absolute and relative frequency of Patients with oxygen therapy during the observational period (see 'Computed variables' chapter)

Percentages will be computed out of the total number of patients evaluable for the FAS.

Table 31. List of oxygen therapies

List of the following variables:

- Patient ID
- "Date of enrollment visit" [[_PatientInfo.Date_enrollment](#)]
- "Kind of therapy" [[F21_OXYGEN_THERAPY.KIND_OF_THER](#)]
- "Drug" [[F21_OXYGEN_THERAPY.DRUG](#)]
- "Flow (L/min)" [[F21_OXYGEN_THERAPY.FLOW](#)]
- "Hours per day" [[F21_OXYGEN_THERAPY.HOURS](#)]
- "Start date of therapy" [[F21_OXYGEN_THERAPY.START_DATE_NF](#)]
- "Ongoing" [[F21_OXYGEN_THERAPY.ONGOING_NF_THER](#)]
- "End date of therapy" [[F21_OXYGEN_THERAPY.END_DATE_NF](#)]
- "Therapy for" [[F21_OXYGEN_THERAPY.NF_THER_FOR](#)]

Only patients evaluable for the FAS will be considered.

Table 32. Patients receiving fixed/non-fixed dose therapies for COPD at enrollment

The table will provide:

- distribution of patients with COPD pharmacological fixed dose therapy at enrollment (see 'Computed variables' chapter);
- distribution of patients with COPD pharmacological non-fixed dose therapy at enrollment (see 'Computed variables' chapter);
- distribution of patients receiving both COPD pharmacological fixed and non-fixed therapy at enrollment (see 'Computed variables' chapter).

Percentages will be computed out of the total number of patients evaluable for the FAS.

Table 33. COPD pharmacological treatments ongoing at enrollment

The table will provide:

- distribution of COPD pharmacological treatments (classes) ongoing at enrollment (see 'Computed variables' chapter).

Percentages will be computed out of the total number of patients evaluable for the FAS.

Table 34. COPD pharmacological treatments ongoing at 6-month follow-up visit

The table will provide:

- distribution of COPD pharmacological treatments (classes) ongoing at 6-month follow-up visit (see 'Computed variables' chapter)

Percentages will be computed out of the total number of patients evaluable for the FAS.

Table 35. COPD pharmacological treatments ongoing at 12-month follow-up visit

The table will provide:

- distribution of COPD pharmacological treatments (classes) ongoing at 12-month follow-up visit (see 'Computed variables' chapter)

Percentages will be computed out of the total number of patients evaluable for the FAS.

Table 36. Medications for adverse events

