The table will provide the distribution of patients according to the field "Therapy for the event" [[F22_AES_AND_ADRS.AE_THERAPY](#)] (i.e. patients who received medications for adverse events during the study).

Percentages will be computed out of the total number of patients evaluable for the FAS.

4.11 Correlation between patients' satisfaction and resource utilization (secondary objective #4)

Table 37. Correlation between patients' satisfaction and resource utilization (including drugs)

A correlation index (Pearson or Spearman) will be computed between TSQM-9 subscales scores (as defined in "Computed variables" chapter) at 12 month follow-up visit and the number of hospitalizations per patient during observation period (as defined in "Computed variables" chapter); p-value will be provided as well.

A correlation index (Pearson or Spearman) will be computed between TSQM-9 subscales scores (as defined in "Computed variables" chapter) at 12 month follow-up visit and the number of ER accesses per patient during observation period (as defined in "Computed variables" chapter); p-value will be provided as well.

A correlation index (Pearson or Spearman) will be computed between TSQM-9 subscales scores (as defined in "Computed variables" chapter) at 12 month follow-up visit and the number of specialist visits per patient during observation period (as defined in "Computed variables" chapter); p-value will be provided as well.

A correlation index (Pearson or Spearman) will be computed between TSQM-9 subscales scores (as defined in "Computed variables" chapter) at 12 month follow-up visit and the number of general practitioner visits per patient during observation period (as defined in "Computed variables" chapter); p-value will be provided as well.

A correlation index (Pearson or Spearman) will be computed between TSQM-9 subscales scores (as defined in "Computed variables" chapter) at 12 month follow-up visit and the number of laboratory test per patient during observation period (as defined in "Computed variables" chapter); p-value will be provided as well.

A correlation index (Pearson or Spearman) will be computed between TSQM-9 subscales scores (as defined in "Computed variables" chapter) at 12 month follow-up visit and the number of therapies administered for COPD per patient during observation period (as defined in "Computed variables" chapter); p-value will be provided as well.

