4.13 Safety

Table 40. Overall Summary of Adverse Events and Adverse Event Reactions

This table will provide:

- the absolute and relative frequency of patients with at least one adverse event (AE) (see 'Computed variables' chapter),
- the absolute and relative frequency of patients with at least one Serious Adverse Event (SAE) (see 'Computed variables' chapter), and
- the patients distribution by "Seriousness Category" [[F22_AES_AND_ADRS.AE_SERIOUSNESS_CAT](#)], and
- the absolute and relative frequency of patients with at least one Adverse Drug Reaction (ADR) to one of the products marketed by Boheringer Ingelheim (namely: Spiriva Handihaler, Spiriva Respimat, Striverdi Respimat, Spiolto Respimat, Oxivent, Dosberotec, Duovent) (see 'Computed variables' chapter), and
- the patients distribution by "Product" [[F22_AES_AND_ADRS.AE_BI_Product](#)]

over the total number of evaluable patients for the Safety set.

Table 41. Patients' distribution by type of adverse event

This table will provide the patients distribution by type of adverse events (i.e. "AE brief description (in English)" [[F22_AES_AND_ADRS.AE_DSCRPT](#)]).

Percentages will be computed over the total number of evaluable patients for the Safety set.

Table 42. Distribution of type of adverse event: details

This table will provide the frequency of each type of adverse events (i.e. "AE brief description (in English)" [[F22_AES_AND_ADRS.AE_DSCRPT](#)]).

Percentages will be computed over the total number of AEs occurred in the Safety set.

Table 43. List of adverse events

The list of all adverse events occurred in the Safety set will be reported. The following variables will be described:

- Patient ID
- "Date of enrollment visit" [[_PatientInfo.Date_enrollment](#)]
- "AE brief description (in English)" [[F22_AES_AND_ADRS.AE_DSCRPT](#)]
- "Date of onset" [[F22_AES_AND_ADRS.AE_ONSET](#)]
- "Is it ongoing at the end of the study?" [[F22_AES_AND_ADRS.AE_ONGOING](#)]
- "End date" [[F22_AES_AND_ADRS.AE_END_DATE](#)]
- "Is it a serious AE" [[F22_AES_AND_ADRS.AE_1](#)]
- "Seriousness category" [[F22_AES_AND_ADRS.AE_SERIOUSNESS_CAT](#)]
- "Is there a reasonable causal relationship with one of the products marketed by BI?" [[F22_AES_AND_ADRS.AE_2](#)]
- "Product" [[F22_AES_AND_ADRS.AE_BI_PRODUCT](#)]
- "Action taken with BI drug" [[F22_AES_AND_ADRS.AE_ACTION](#)]
- "Therapy for the event" [[F22_AES_AND_ADRS.AE_THERAPY](#)]
- "Outcome of the event" [[F22_AES_AND_ADRS.AE_OUTCOME](#)]

[figure not shown]

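### SAP Table 40 divides sponsor-product ADRs by a Safety set that does not exclude non-users, with no user count described, and the safety tables omit events in consented patients who fail two data checks

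*SAP*

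**What the plan says.** One line of SAP section 4.13, Table 40, is "the absolute and relative frequency of patients with at least one Adverse Drug Reaction (ADR) to one of the products marketed by Boheringer Ingelheim". Another line breaks patients down by product. Each is expressed "over the total number of evaluable patients for the Safety set". The ADR flag (SAP section 3) and the product field come from the adverse-event log, not from the therapy log.

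SAP section 2.4 defines the Safety set as "All enrolled patients meeting the inclusion criteria #4 and #5 and not meeting the exclusion criteria #7, #8 and #9". Its explanatory gloss describes "all enrolled subjects who provided informed consent to both participation in the study and privacy form" with a need for guideline-based regular treatment. Protocol section 9.2 asks for patients "undergoing stable pharmacological treatment for COPD since at least 3 months" and names no product.

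On treatment use, Table 33 gives the "distribution of COPD pharmacological treatments (classes) ongoing at enrollment"; Tables 34 and 35 do the same at the follow-up visits, and Table 32 splits fixed from non-fixed therapy. For these tables, and for Table 36 on medications for adverse events, the SAP says "Percentages will be computed out of the total number of patients evaluable for the FAS".

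On the listing, Table 43 states: "The list of all adverse events occurred in the Safety set will be reported". Tables 41, 42 and 44 have the same restriction. Protocol section 11.2 collects ADRs, fatal adverse events and pregnancies from consent onwards, for the sponsor product taken for COPD.

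**The concern.** A patient who never took a sponsor product cannot have an ADR to one, yet nothing keeps that patient out of the denominator. The numerator belongs to users and the denominator to everyone in the set. A reader could take the percentage as the ADR risk of the sponsor's products, although it also moves with prescribing share, and that share is not printed in any table described.

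The second issue is coverage. An event entered in the eCRF for a consented, treated patient can drop out of every safety table because a therapy start date is missing or because two forms carry different dates. Neither is a reason to leave an event out of a listing.

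**Working it through.** The documents give no ADR rate, user share or Safety-set size, so there is no planned figure to reproduce. The check traces the definitions and then illustrates size on stated assumptions.

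**1. Does the Safety set condition on use?** Section 2.4 applies criteria 4 (stable COPD treatment), 5 (consent and privacy form), 7 (no drug trial), 8 (not treatment-naive) and 9 (no ACOS). None refers to a sponsor product.

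**2. Can a reader recover the user share?** Table 32 gives fixed and non-fixed therapy. Tables 33 to 35 give drug classes over the FAS. The product row of Table 40 counts products attached to events. None counts users. The section 5 layouts are not in the text available for this review; the titles listed for them name no product-user table.

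**3. Size of the dilution.** If ADRs occur only in users, shown % = risk among users × user share. N = 400 is the planned enrolment (protocol section 9.5). The 5% risk and the shares are assumptions.

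| User share | Over users | Over Safety set |
|---|---|---|
| 20% | 4/80 = 5.0% | 4/400 = 1.0% |
| 40% | 8/160 = 5.0% | 8/400 = 2.0% |
| 60% | 12/240 = 5.0% | 12/400 = 3.0% |
| 80% | 16/320 = 5.0% | 16/400 = 4.0% |
| 100% | 20/400 = 5.0% | 20/400 = 5.0% |

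By product at the same 5% risk, a 30% share gives 6/120 = 5.0% against 6/400 = 1.5%. A 5% share gives 1/20 = 5.0% against 1/400 = 0.25%. A percentage on 20 users says little, so product rows are better shown as n/N.

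**4. Who falls outside the safety tables?** The criterion numbers in section 2.4 follow section 2.1. Criterion 4 as programmed there requires a non-missing therapy start date. Criterion 5 requires the consent date to equal the privacy-form date. The section 2.4 gloss asks only that both were given. A patient who signed the two forms on different days meets the gloss and fails the check. Table 36 does not recover these events: the FAS requires criteria 1 to 10, so it is a subset of the Safety set. A death might still appear as a drop-out cause in Table 3, which covers all enrolled patients.

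**5. Size of the listing gap.** Expected unlisted patients = number outside the set × share with a recorded event. Neither input is in the documents. For 10, 20 or 40 patients outside and a 5% event share, the result is 0.5, 1 or 2. The range runs from 10 × 2% = 0.2 to 40 × 10% = 4.

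**6. How should users be counted?** Take 160 true users with 8 ADRs, and suppose 10% of users lack a therapy record. If every ADR patient is counted as a user regardless, the denominator is 152 × 0.9 + 8 = 144.8, and 8/144.8 = 5.5%, not 5.0%. Exposure would then depend on outcome and the figure would rise. With matched records only, 7.2/144 = 5.0%. Ten old records wrongly counted as use would give 8/170 = 4.7%, a small shift beside 8/400 = 2.0% under the planned denominator.

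**The case against.** The strongest reply is that nothing is mislabelled. The SAP states its denominator and prints absolute counts, and Tables 1 and 2 show the Safety-set size and the reasons for non-eligibility. No objective concerns safety. Protocol section 9.7 pools all treatments, and section 9.13 disclaims any causal or treatment-related inference. Expedited reporting under protocol section 11.2 runs separately. All of this stands, and it is why the priority is minor. It does not supply the missing user count, and a matching denominator requires no comparison between products.

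A second reply is that protocol section 9.6 excludes eligibility violators from analyses. A reader might infer that leaving any consented patient out of Table 43 is an error. The documents do not support that: for true violators of criteria 4, 7, 8 or 9 the exclusion has a protocol basis, and section 2.4 is already more inclusive than section 9.6 because it does not apply criteria 1, 2, 3 and 6. The gap concerns patients removed on data grounds. Even there, the gloss leaves it unclear whether the same-date check is meant to govern the Safety set.

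**Conclusion.** The point holds as a minor, inexpensive improvement. The Safety set does not exclude patients who never used a sponsor product, and no table described counts users. If there are non-users, the Table 40 ADR percentage is the users' risk scaled by an unreported share. A reader might go further and conclude that the set does include non-users and that the percentage understates the risk. The documents do not show this: the share is not given, and if every patient is a user there is no dilution. A section 5 layout might also add a count.

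On the listing, events in consented, treated patients who fail the start-date or same-date check appear in no safety table, if those programmed checks govern the Safety set. The assumed range is 0.2 to 4 patients, and the true number could be zero.

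A reader might also infer that the AE and SAE rows hold only the events named in protocol section 11.2. The adverse-event form has a separate yes/no causality field (SAP section 3), so unrelated events may be recorded too. The documents do not settle this.

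**What to change.** 1. **Table 40.** Keep the Safety-set counts. Add the number of Safety-set patients with a sponsor-product record in the therapy log that overlaps observation, overall and by product, and give ADRs as n/N over those users. Overlap can mean a start on or before the end of observation, with either an end date on or after consent, or a missing end date and the ongoing-at-end field set to yes. Do not reuse the SAP section 3 rule for counting therapies and switches: it misses a drug ongoing at enrolment and stopped during observation.
2. **Unmatched ADRs.** Before database lock, query any ADR patient with no matching therapy record. Report unresolved cases separately and do not add them to the denominator.
3. **Table 43.** List events for all consented enrolled patients, flag those outside the Safety set, and document this as a listing-only departure from protocol section 9.6.
4. **Criterion 5.** Reconcile the same-date check with the consent wording of section 2.4.

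Add no footnote limiting the AE and SAE rows to the protocol section 11.2 scope unless the eCRF confirms that scope.

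The cost is product-level coding of seven products, one user flag, one listing column and a short note. The coding goes beyond the planned class coding, which omits therapies for exacerbations and COPD-related adverse events. The downside is smaller denominators, with possibly very few users of some products.

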The following must be reported by the investigator on the NIS AE form (or pregnancy monitoring form if applicable) from signing the informed consent onwards until the end of the study for the BI product administered for the disease in scope of the study:

| Type of Report | Timeline |
|-----------------------------------|-----------------------------|
| All SADRs | immediately within 24 hours |
| All AEs with fatal outcome | immediately within 24 hours |
| All non-serious ADRs | 7 calendar days |
| All pregnancies | 7 calendar days |

The same timelines apply if follow-up information becomes available for the respective events. In specific occasions the Investigator could inform the Sponsor upfront via telephone. This does not replace the requirement to complete and fax the NIS AE form.

Information required

For each reportable adverse event, the investigator should provide the information requested on the appropriate (e)CRF pages and the NIS AE form.

Reporting of related Adverse Events associated with any other BI drug

The investigator is encouraged to report all adverse events related to any BI drug other than the BI drug taken for the disease in scope of the study according to the local regulatory requirements for spontaneous AE reporting at the investigator's discretion by using the locally established routes and AE report forms. The term AE includes drug exposure during pregnancy, and, regardless of whether an AE occurred or not, any abuse, off-label use, misuse, medication error, occupational exposure, lack of effect, and unexpected benefit.

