The Morisky medication Adherence Scale 4 items (MMAS-4) is a self-reported, medication-taking behavior scale and consists of four questions about the way patients might experience drug errors or omissions. Each item [F13_MMAS_4.MMAS_4_1 - MMAS_4_4] has a scoring scheme of "Yes" = 0 and "No" = 1. Items are summed to give a non-adherence score ranging from 0 to 4; a higher score means better adherence to therapy (Morisky DE, Green LW, Levine DM. Concurrent and predictive validity of a self-reported measure of medication adherence. *Med Care*. 1986 Jan;24(1):67-74).

The score can be calculated if at least 3 out of 4 of the items are completed. If only one item is omitted, the value for the missing item is the group median of this item that has been completed by all eligible participants. This median value will be imputed for all eligible cases who did not answer this item.

Changes in the MMAS-4 score at each follow-up visit from enrollment will be calculated, for each patient, as the following difference: (score at 6/12 months - score at enrollment), if both scores are available.

COPD pharmacological treatments (classes) ongoing at enrollment

All COPD pharmacological treatments having "End date of therapy" [F20_COPD_PHARMACOLOGICAL_THERAPY.END_DATE_THER] > "Date of enrollment visit" [PatientInfo.Date_enrollment] OR ("End date of therapy" missing and "Ongoing at the end of observation?" [F20_COPD_PHARMACOLOGICAL_THERAPY.ONGOING_THER] = "Yes").

Drug names will be coded by CDM and grouped according to the following categories:

- LAMA alone
- LABA alone

- ICS alone
- LABA + LAMA (Fixed dose combination or not)
- LABA + ICS (Fixed dose combination or not)
- LABA + LAMA + ICS
- SABA or SAMA on demand
- Other: pharmacological therapies for COPD not included in the previous classes.

Categories above are not mutually exclusive: a patient could be classified in more than one category (i.e. if a patient is receiving LABA and SABA on demand, [REDACTED] will be classified both in the “LABA alone” and in the “SABA or SAMA on demand” classes). Only therapies for COPD will be considered (i.e. those records with field Therapy for [F20_COPD PHARMACOLOGICAL THERAPY.THERAPY_FOR] = “COPD”), while therapies for COPD exacerbations or for COPD-related adverse events will not be considered nor classified.

COPD pharmacological treatments (classes) ongoing at 6- and 12-month follow-up visit

At each follow-up visit, all COPD treatments classes (see algorithm above) having

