- **Table 38. Exacerbations: patients' distribution:** Table output will be verified by another BS or CDM ; moreover, randomly chosen patients (20% of evaluable patients) will be checked by a CDM or another BS in order to assess whether Number of exacerbations per patient during observation period is correctly computed according to the algorithm described in the SAP
- **Table 40. Overall Summary of Adverse Events and Adverse Event Reactions:** Table output will be verified by another BS or CDM ; moreover, randomly chosen patients (10% of evaluable patients) will be checked by a CDM or another BS in order to assess whether patients with at least one AE/SAE/ADR were correctly identified according to the algorithm described in the SAP
- **Table 43. List of adverse events:** 3 patients will be verified with respect to DB content
- **Table 45. Patients' satisfaction for medical treatment (TSQM-9 items) at each study visit - Switchers vs non-switchers:** randomly chosen patients (50% of evaluable patients) will be checked by a CDM or another BS in order to assess whether they were correctly classified as switchers/non-switchers.

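### SAP Tables 41 and 42 count adverse events by the eCRF description field and the available text states no coding step, so differing wordings of one event would split the by-type rows

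*SAP*

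**What the plan says.** SAP 4.13 plans four outputs that bear on this point.

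- **Table 40** gives patients with at least one AE, SAE or ADR, and distributions by seriousness category and by product.
- **Table 41**: "This table will provide the patients distribution by type of adverse events". The type is specified, after an explicit "i.e.", as the field AE_DSCRPT (label "AE brief description (in English")). On the denominator: "Percentages will be computed over the total number of evaluable patients for the Safety set".
- **Table 42**: "This table will provide the frequency of each type of adverse events", with the same field in the same role. Here the denominator is the number of events: "Percentages will be computed over the total number of AEs occurred in the Safety set".
- **Table 43** lists every event, showing the same description field beside seriousness, causal relationship, product, action taken and outcome.

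On who supplies the entry, Protocol 11.2 says: "For each reportable adverse event, the investigator should provide the information requested on the appropriate (e)CRF pages and the NIS AE form".

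SAP section 3 does state a coding step for medication: "Drug names will be coded by CDM and grouped according to the following categories". It has no matching sentence for adverse event terms.

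**The concern.** A table by type is useful only if the same event always falls in the same row. Here the row is defined by a description field, and about 20 Italian centres (Protocol 9.1) supply the entries in English. Spelling, synonyms and translation can all vary between centres. A programmer following SAP 4.13 literally would count each distinct string as a type.

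Three effects would follow if wordings differ: more types than really occurred, fewer patients or events in each, and a patient who reported the same event twice in different words counted under two types in Table 41. Tables 41 and 42 are the only adverse event summaries by type in the plan, so no other table would show the combined count for an event.

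**Working it through.** **1. Is a coding step stated anywhere in the available text?**

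| Place | What it gives on adverse event terms |
|---|---|
| Protocol 9.6 (data management) | Entry review, queries and lock; no term coding |
| Protocol section 11 | Definitions, collection, causality, intensity, reporting times; no dictionary |
| SAP section 3 | Identifies patients with an AE by the description being non-missing; coding is stated for drug names only |
| SAP 4.13 | Names the description field as the type in Tables 41 and 42; no coded term, preferred term or body system |
| SAP section 6 | Quality checks; no term coding |

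CTCAE is in the protocol's abbreviation list, but the safety text does not use it.

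**2. Would the planned checks pick the problem up?** The SAP section 6 list of tables to be reprogrammed or independently verified includes Tables 40 and 43 but not 41 or 42. For Table 43 the check is: "3 patients will be verified with respect to DB content". All tables also get a general review for consistency and plausibility. A correct count of distinct strings would be consistent with the database, so such a review might notice obvious variants but need not.

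**3. How large could the split be?** The plan gives no adverse event count or rate, so there is no figure of its own to reproduce. What follows is illustration only.

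Inputs: N = 400, the approximate planned enrolment (SAP section 1), as an upper scale for the Safety set. Assumed: a reaction in n patients, k different wordings, one wording per patient.

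The k rows sum to n, so the largest row holds at least ceil(n/k) patients. That minimum is reached under an even split, which is the worst case for a given k. The displayed percentage is then 100 × ceil(n/k)/N, against a true 100 × n/N.

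| n (true %) | k = 2 | k = 3 | k = 4 |
|---|---|---|---|
| 8 (2.00%) | 4 (1.00%) | 3 (0.75%) | 2 (0.50%) |
| 20 (5.00%) | 10 (2.50%) | 7 (1.75%) | 5 (1.25%) |
| 40 (10.00%) | 20 (5.00%) | 14 (3.50%) | 10 (2.50%) |

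Over this assumed range, the largest row shows 0.50% to 5.00% where the true rate is 2.00% to 10.00%. An uneven split costs less: 20 patients worded as 17, 1, 1 and 1 give a largest row of 17/400 = 4.25% against 5.00%. With k = 1 there is no loss.

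The same logic applies to Table 42 with events in place of patients. Neither denominator depends on wording; only the numerators of the by-type rows do.

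**4. What is not touched?** Table 40 uses non-missing records, yes/no flags and categorical fields, so its counts do not change with wording. Table 43 prints every event.

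**The case against.** The strongest reply is that much of this is inferred from documents that are not available. The eCRF is not provided, so the field's format is not known for certain. The Data Management Plan, the Data Validation Plan and the contractor's procedures are cited but not supplied, and the table layouts in SAP 5.13 are not shown. Coding could be described in any of them. The drug-name contrast is also weak evidence, because that step exists to build treatment classes and does not show that coding of events was rejected.

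This limits the point in two ways. A reader might infer that adverse events in this study are not coded at all. The documents do not support that: they show only that no coding is stated in the available text. A reader might also take the field as proven free text. The label, with its instruction to write in English, makes that likely but does not establish it. What survives is that SAP 4.13 names the description field, not a coded term, as the row variable. Even if a coded variable exists, the SAP as written does not use it.

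A second reply concerns harm. A reader might infer that a repeated reaction to one product could be hidden. That goes too far. Tables 41 and 42 are not split by product or causality, so coding them would not show reactions by product either. Table 40 already counts patients with an ADR and gives the product distribution, and Table 43 lets a reader regroup synonyms. Individual cases are also reported separately under Protocol 11.2, within 24 hours or 7 days depending on the type of report. This reply stands.

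Third, safety is neither a primary nor a secondary objective, and Protocol 11.2 limits required collection to ADRs, fatal AEs and pregnancies for the sponsor's product. That bounds the importance of the point. It does not make the two tables correct.

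**Conclusion.** The point holds in a conditional and narrow form. SAP 4.13 gives an explicit tabulation rule that would split one event over several rows wherever its wording differs, and the available text contains no step that would prevent this. Counts per type may be understated and the number of types inflated.

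This rests on two assumptions: that the field holds verbatim text, and that wordings do differ between reports. A reader might take a four-fold understatement (2.00% shown as 0.50%) as the expected size. The documents do not support any particular size. That figure needs four wordings in equal numbers, and both are assumed.

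The effect is confined to the by-type rows of two descriptive safety tables. No study objective, primary or secondary estimate, or overall AE, SAE or ADR total changes.

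**What to change.** State in the SAP that adverse event descriptions are coded before database lock with a named medical dictionary and version, for example MedDRA preferred term and system organ class. Then:

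- **Table 41**: tabulate by coded term, counting each patient once per term.
- **Table 42**: tabulate events by coded term.
- **Table 43**: print the verbatim description beside the coded term.

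If the Data Management Plan already provides for coding, cite it and replace AE_DSCRPT with the coded variable in Tables 41 and 42. In that case only the SAP wording changes.

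The cost is a few sentences in the SAP, plus coding and a coding review of the adverse event records before lock. The data manager already codes drug names, so the task falls within an existing function. No new data are collected.
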